RSA	Resting/Baseline Heart Rate Variability
SAE	Serious Adverse Event
SCS	Self-Compassion Scale
SSD	Schizophrenia spectrum disorder
TAU	Treatment as usual
UNC	University of North Carolina at Chapel Hill
WASI	Wechsler Abbreviated Scale of Intelligence

PROTOCOL SYNOPSIS

Study Title	Targeting Stress Reactivity in Schizophrenia: Integrated Coping Awareness Therapy (I-CAT)
Funder	National Institutes of Health
Clinical Phase	Phase I
Study Rationale	The purpose of the I-CAT trial is to test the feasibility of a psychosocial intervention that combines mindfulness, positive psychology, and determine the effectiveness of this intervention on the physical and mental health for individuals with schizophrenia spectrum disorders.
Study Objective(s)	
 1. Feasibility- Can I-CAT be delivered within this treatment setting? 2. Tolerability- How well is I-CAT accepted by the subjects? 3. Intervention adherence 4. Evaluation of I-CAT
Test Article(s) (If Applicable)	FirstBeat HR Bodyguard 2 devices, will be utilized to monitor heart-rate variability at rest and while engaging in mindfulness activities.
Study Design	This is a two arm, randomized controlled trial with 40 subjects (20 assigned to I-CAT and 20 assigned to TAU).
Subject Population	Inclusion Criteria
key criteria for Inclusion and Exclusion:	
 1. DSM-V diagnosis of a SSD (Schizophrenia, Schizoaffective Disorder, Brief Psychotic Disorder, Schizophreniform Disorder, and Unspecified Schizophrenia Spectrum and Other Psychotic Disorder) 2. Less than 8 years of antipsychotic and/or psychological treatment for psychosis 3. Between the ages of 18-35, both genders, and any ancestry 4. IQ>80. IQ will be assessed using the Wechsler Abbreviated Scale of Intelligence (WASI) 5. Does not meet current substance dependence criteria 6. No hospitalizations for psychiatric reasons in the last 3 months 7. Not actively practicing meditation (not taking a workshop or practicing meditation in the past year) 8. Clinically stable (no psychiatric medication changes within the past month and on medication regimen not anticipated to change during the next 6 months) 9. Willing and able to provide informed consent.
Number of Subjects	40 individuals with schizophrenia spectrum disorders

Study Duration	Each subject’s participation will last 12 months, 9 months of intervention and a 3-month follow-up
Study Phases Screening Study Treatment Follow-Up	
Pre- Screening- Will be completed prior to the first in-person visit via a telephone screen for study eligibility.
 
Screening- Subjects who are deemed eligible will be brought on site to obtain consent and complete the screening assessments (Demographics, Wechsler Abbreviated Scale of Intelligence [WASI], Perceived Stress Scale [PSS]).
 
Baseline - Subjects will complete the Daily Stress Inventory (DSI), Five Facets of Mindfulness (FFMQ), modified Differential Emotions Scale (mDES), Perceived Well Being (PWB), short Self Compassion Scale (short SCS), First Episode Social Functioning Scale (FESFS), Positive and Negative Syndrome Scale (PANSS), abbreviated Quality of Life Scale (QLS). Subjects will also provide saliva samples every half hour over 2.5 hours for the measurement of cortisol. Additionally, subjects will wear the FirstBeat device to provide heart rate variability while resting and during a mindfulness activity.
 
Mid-Treatment - Subjects will complete the FFMQ, mDES, PWB, short SCS, FESFS, PSS, PANSS, and the QLS).
 
Post-Treatment – Subjects will complete the DSI, FFMQ, mDES, PWB, short SCS, FESFS, PSS, PANSS, QLS. Subjects will also provide saliva samples every half hour over 2.5 hours for the measurement of cortisol. Additionally, subjects will wear the FirstBeat Bodyguard 2 device to provide heart rate variability while resting and during a mindfulness activity. At the conclusion of the trial, investigators will administer a brief questionnaire to the subjects regarding satisfaction and acceptability.
 
3-Month Follow-up – Subjects will complete the FFMQ, mDES, PWB, short SCS, FESFS, PSS, PANSS, and QLS.
 
Study Treatment- Subjects will participate in individual therapy sessions (I-CAT or TAU) weekly or bi-weekly for 60 minutes.

Efficacy Evaluations	
Primary outcome – Psychological - Least means change from baseline scores at mid-treatment, post-treatment, and follow-up on positive emotions (mDES), role functioning (QLS, FESFS), and stress reactivity (PSS, DSI).
 
Primary outcomes – Biological - Least means change from baseline to post-treatment on salivary cortisol.
 
Secondary outcomes- Psychological- Least means change from baseline scores at mid-treatment, post-treatment, and follow-up on psychiatric symptoms (PANSS), mindfulness (FFMQ, short SCS), and well-being (PWB).

	
Secondary outcomes- Biological- Least means change from baseline to post-treatment on resting/baseline heart rate variability (RSA).

Safety Evaluations	
A safety plan for the intervention sessions will be developed prior to the initiation of the study with [name], as well as the study clinicians.

Statistical and Analytic Plan	
Analyses will focus on average change over time (i.e., change from baseline scores) on primary outcomes (positive emotions, role functioning, stress reactivity, salivary cortisol) and secondary outcomes (psychiatric symptoms, mindfulness, well-being, heart rate variability). Analyses will utilize hierarchical linear models with random intercepts for each subject that will estimate the average change from baseline (i.e., least means change) for each treatment group (TAU, I-CAT) at mid-treatment, post-treatment, and follow-up timepoints.

DATA AND SAFETY MONITORING PLAN	
[name] will function as the Project Medical Officer. An independent physician will serve as the Medical Monitor ([name], from the Department of Psychiatry).

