3 ASSESSMENT OF DATA

At this stage of treatment development, specific outcomes include:

1. Feasibility- Can I-CAT be delivered within this treatment setting?
 - a. Attrition rates
2. Tolerability- How well is I-CAT accepted by the subjects?
 - a. I-CAT feedback survey outcomes
3. Intervention adherence
 - a. Attendance rates, session fidelity ratings
4. Evaluation of I-CAT
 - a. Primary and secondary outcomes will be compared between I-CAT and TAU

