3.1 OUTCOMES

The central hypothesis is that I-CAT will increase positive emotions, increase role functioning, and decrease stress reactivity as measured by self-report measures and salivary cortisol. Secondary hypotheses are that I-CAT will decrease psychiatric symptoms, increase mindfulness, and increase well-being as measured by self-report, clinical interview measures, and heart rate variability. Guided by strong preliminary data, this hypothesis will be tested via four specific aims:

1. To examine the feasibility of implementing I-CAT at a community mental health clinic
2. To examine the tolerability of I-CAT at a community mental health clinic
3. To examine I-CAT adherence through attrition and attendance rates
4. We will also examine the impact of I-CAT on primary outcomes (positive emotions, role functioning, stress reactivity), and secondary outcomes (psychiatric symptoms, mindfulness, well-being) compared with TAU.

We hypothesize that I-CAT will be associated with:

- Improved primary outcomes including increased positive emotions, increased role functioning, and decreased stress reactivity at mid-point, post-test, and three-month follow-up.

- Improved secondary outcomes including decreased psychiatric symptoms, increased mindfulness, and increased well-being at mid-point, post-test, and three-month follow-up.

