5 STATISTICAL ANALYSES

5.1 DATA ANALYTIC PLAN

Feasibility will be defined by our ability to meet our recruitment targets (40 people), frequency of engagement in the intervention by participants (session attendance and attrition rates), and feedback on the intervention from I-CAT participants.

Differences between group demographics to check effectiveness of randomization will utilize independent samples t-tests (continuous variables) or Pearson chi-square tests (categorical variables). Little's Missing Completely at Random test will be performed to establish whether data is missing at random and to determine if data imputation will be needed for subsequent analyses.

To test whether intervention groups differ in their amount of change on treatment outcomes over time, data will be analyzed according to the intent-to-treat principle, in which all subjects randomized will be included in the analysis. To examine intervention effects on primary and secondary outcomes, linear mixed-effects models will be utilized with restricted maximum likelihood estimation where missing data will be handled via full information maximum likelihood. The linear mixed-effects models will include effects of time (i.e., baseline, mid-treatment, post-treatment, and follow-up), intervention group, and a group by intervention interaction with random intercepts to account for baseline differences on outcome variables. Observations classified as outliers (i.e., residual values less than or greater than 1% of all observations) will be excluded. Changes from baseline will be estimated using least-squares means for each intervention group.

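### Tolerability rests on one feedback survey whose only stated timing is the end of the trial, and nothing secures answers from subjects who withdraw earlier, so acceptability may be overstated

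*Combined protocol and SAP*

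**What the plan says.** Section 3 and the synopsis list tolerability as the second of four objectives: "Tolerability- How well is I-CAT accepted by the subjects". Section 3 gives it one measure: "I-CAT feedback survey outcomes". Section 5.1 uses the same kind of information again, as part of the definition of feasibility: "frequency of engagement in the intervention by participants (session attendance and attrition rates), and feedback on the intervention from I-CAT participants".

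The only statement of when subjects are asked is in the synopsis, Study Phases, under Post-Treatment: "At the conclusion of the trial, investigators will administer a brief questionnaire to the subjects regarding satisfaction and acceptability". The measure lists in Sections 4.2.2 (baseline and post-treatment) and 4.2.3 (mid-treatment and follow-up) do not include a satisfaction, acceptability or feedback instrument.

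Attrition and attendance are collected, but under other headings. Section 3 puts attrition under feasibility and attendance under intervention adherence. Aim 3 in Section 3.1 is "To examine I-CAT adherence through attrition and attendance rates".

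For treatment outcomes, Section 5.1 states that "data will be analyzed according to the intent-to-treat principle, in which all subjects randomized will be included in the analysis". No corresponding statement is made for the survey.

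**The concern.** Subjects who leave early may include those who found I-CAT hardest to accept, and a questionnaire given once at the end is least likely to reach them. The protocol expects some to leave. Attrition is a listed outcome, Section 7.2 provides for subjects who withdraw or are discontinued because of a serious adverse event, and the consent check in Section 9 asks what subjects would do if they no longer wished to take part. Section 6 also names anxiety from discussing stressors as a risk of I-CAT, which could plausibly lead someone to stop.

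If the survey is answered mainly by finishers, it describes acceptability among those who stayed, whereas the objective asks about the subjects. Section 2.1 presents the trial as preparation for a larger one, so acceptability is one of its main products. Feedback not collected when a subject leaves may not be recoverable later, and no analysis can replace it.

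**Working it through.** **No stated figure to reproduce.** The documents give no expected attrition, no scoring of the survey, no definition of a satisfied subject and no acceptability threshold. The check is therefore a reading of the provisions, followed by an illustration.

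**The provisions side by side**

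| Question | What the documents give |
|---|---|
| Measure of tolerability | I-CAT feedback survey only (Section 3) |
| Timing | Once, at the end (synopsis, Post-Treatment), for a satisfaction and acceptability questionnaire |
| Place in the visit schedule | None (Sections 4.2.2 and 4.2.3) |
| Survey on stopping or withdrawal | None |
| Reason for stopping therapy | Not collected under any section |
| Denominator, or handling of survey non-response | None (Section 5.1) |

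The intent-to-treat rule and the likelihood-based handling of missing data in Section 5.1 are written for change on the primary and secondary outcomes. The survey is neither.

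**Illustration.** The arm size comes from the synopsis: "20 assigned to I-CAT and 20 assigned to TAU". All other inputs are assumptions. Let k be the number of I-CAT subjects who leave and do not answer, p_f the proportion satisfied among finishers and p_l the proportion satisfied among leavers.

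- Acceptability among all randomised to I-CAT = [(20 − k) × p_f + k × p_l] / 20
- Overstatement by the finisher-only figure = p_f − that value = (k / 20) × (p_f − p_l)

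With p_f = 80%:

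| k | All-subject rate, p_l = 0 | Overstatement | All-subject rate, p_l = 50% | Overstatement |
|---|---|---|---|---|
| 2 | 72% | 8 points | 77% | 3 points |
| 4 | 64% | 16 points | 74% | 6 points |
| 6 | 56% | 24 points | 71% | 9 points |
| 8 | 48% | 32 points | 68% | 12 points |

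For example, with k = 4 and p_l = 0: (16 × 0.80 + 4 × 0) / 20 = 12.8 / 20 = 64%, and 80 − 64 = 16 points. The rates are expected proportions, so the implied counts need not be whole numbers.

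With p_f = 90% and k = 4, the all-subject rate is 72% if no leaver is satisfied (18 points) and 82% if half are (8 points).

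When p_l = p_f, or when the leavers answer (k = 0), the overstatement is zero. Each subject in the arm is worth 1/20 = 5 points.

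**The case against.** A reader might infer that early stoppers are excluded and that the tolerability result is bound to be too high. The documents do not support that, for four reasons.

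- **Stopping therapy is not the same as leaving the study.** The questionnaire goes to the subjects, with no restriction to finishers, and no section says that ending sessions ends assessment visits. Section 4.1.1 lets I-CAT run from 14 to 24 sessions, so subjects may finish at different times and still attend post-treatment. This stands. The gap concerns chiefly those who withdraw before the post-treatment visit.
- **There may be two instruments.** Section 3 names a feedback survey specific to I-CAT, while the synopsis describes a questionnaire for the subjects generally. They are probably the same, but this is not stated. If they differ, the timing of the feedback survey is not given at all, and the remedy is the same.
- **Early stopping is visible elsewhere.** Attrition and attendance are reported, Section 5.1 names them together with "feedback on the intervention from I-CAT participants", and Section 7.1 tracks adverse events. A reader would therefore see the number of leavers beside the survey result, which weakens the concern. It does not remove it: a count without reasons cannot separate dislike of I-CAT from, say, relocation, and no rule says how to read the two together.
- **The direction and size are assumed.** Leaving need not reflect poor acceptance. Setting every leaver to not satisfied is a worst case that largely restates attrition. This also stands, which is why the range above includes zero and why the worst case should not be the headline figure.

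It can also be said that no acceptability threshold or go/no-go rule depends on this figure. That is correct, and it limits the consequence to how the result is interpreted.

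**Conclusion.** The point holds as a risk that the plan leaves open. Tolerability has one listed measure. The only timing given for such a questionnaire is the end of the trial, and nothing secures an answer from a subject who withdraws before the post-treatment visit. A figure drawn mainly from finishers may overstate acceptability.

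On the assumptions shown (20 in I-CAT, 80% of finishers satisfied, 2 to 8 leavers not responding), the overstatement is 3 to 12 points if half the leavers are satisfied and 8 to 32 points if none are. It is zero if leavers respond or share the finishers' view. Attrition and leavers' views are not in the documents, so no value in this range can be called expected. The change is worth making because it is cheap, it affects a named objective, and the missing answers may not be obtainable afterwards.

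**What to change.** **Section 4.2 and synopsis.** State whether the feedback survey and the satisfaction questionnaire are the same instrument, and add it to the schedule. Offer it to every I-CAT subject at the earlier of stopping or withdrawal or the post-treatment visit, with one added item on the main reason for stopping. Allow completion by telephone or in Qualtrics, which Section 5.3 already uses.

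**Section 5.1.** Report the number responding and the number satisfied out of all randomised to I-CAT, beside attrition. Give the respondent-only figure. Next to it, and only as a conservative bound, give the figure with non-responding leavers counted as not accepting.

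**Cost.** A few extra contacts, one added item, and short additions to Section 4.2, Section 5.1 and the synopsis. Some leavers will still not respond, and the tolerability figure may turn out less favourable.

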1 BACKGROUND AND RATIONALE

Affecting one out of every one hundred people, schizophrenia is a common and all-too-often devastating disorder ([name], 2011). Florid psychotic symptoms respond well to available antipsychotic medication. People can recover in the early stages of illness; however with repeated relapse, persons with schizophrenia typically develop residual deficits that interfere with the ability to achieve a sustained, full recovery such that less than 20%, of those affected avoid disability (Lambert et al., 2006; Robinson et al., 2004). Residual impairments include negative symptoms, such as low motivation and drive, social withdrawal, and reduced hedonic capacity, as well as social and cognitive deficits. We add to the list of residual impairments a dysregulated stress response, as indexed by endocrine (Walker et al., 2008), autonomic (Castro et al., 2008; Chang et al., 2009; Lee et al., 2006; Sarosi, 2006), and immune (Miller et al., 2011) parameters. The costs of residual impairments and psychotic relapse are enormous—schizophrenia ranks as the third leading cause of disability-adjusted life years lost for young persons under the age of 24 (Gore et al., 2011). The cost of direct treatments for persons with schizophrenia is almost 3% of total health care expenditures driven by relapse, re-hospitalization, and residential treatment costs (Knapp et al., 2004).

Epidemiological studies clearly establish that stressful life events precede the onset of the first episode and occurrence of psychotic relapse (van Os et al., 2005; van Os et al., 2010; Broome et al., 2005; Brown et al., 2011; Nuechterlein et al., 1984; Thompson et al., 2007; McEwen et al., 2000). Observational studies consistently find alterations in autonomic (Sarosi et al., 2006; Castro et al., 2008), endocrine (Walker et al., 2008), and immune system (Miller et al., 2011) function in persons with schizophrenia and their first degree relatives, consistent with a dysregulated stress response. In agreement with these studies, we find that persons with first episode schizophrenia have elevated afternoon basal cortisol and a blunted cortisol response to a mental arithmetic stressor (Figure 1a). Similarly, we find a dysregulated cardiovascular response to the same stressor (Figure 1b-c). Persons who develop schizophrenia may suffer allostatic overload, defined as the physiological consequences or “wear and tear” on the body in response to repeated stressful situations (McEwen, 2000), for several possible reasons. They have a greater likelihood of exposure to stressful events such as childhood trauma, which corresponds to an increased sensitivity to stress and difficulties regulating the stress response (Lardinois et al., 2011; van Winkel et al., 2008). In addition, consequences of acute psychosis (e.g., disrupted social relationships) are significant stressors. There also is evidence that persons with schizophrenia may have an innate low capacity to respond to stressors (Ventura et al., 1989; Zubin et al., 1977), and thus even daily hassles and routine stressors may lead to allostatic overload.

We theorize that allostatic overload in persons with schizophrenia contributes to the severity of neurocognitive and social cognitive deficits that are most strongly associated with impaired function. Furthermore, we propose that impaired stress reactivity underlies the observed relationship of stressful life events and psychotic relapse. We further theorize that, as with healthy individuals under chronic stress, impaired stress reactivity contributes to the medical morbidity associated with schizophrenia, including high risks of cardiovascular disease and premature death. Despite the compelling evidence of dysregulated stress reactivity in persons with schizophrenia, translational studies investigating mechanisms and intervention studies targeting stress reactivity are lacking. Thus, we hypothesize that an intervention to ameliorate and improve impaired stress reactivity will change the trajectory of schizophrenia and reduce the likelihood of chronic disability and the associated medical morbidity.

Although the importance of stress in the etiology of schizophrenia has been well established (Walker et al., 2008; Corcoran et al., 2003), there is a critical lack of approaches that specifically target the dysregulated stress response in treatment. Pharmacological treatments target psychotic symptoms but do not prevent disability. Psychosocial treatments for schizophrenia such as illness self-management approaches, cognitive

behavioral therapy (CBT), and cognitive remediation are aimed at improving the proximal deficits surrounding symptoms, relapse, and cognitive impairments, but these treatments often have only small to moderate effects on long-term functional recovery (Dixon et al., 2010). None of these interventions directly address impaired stress reactivity that we theorize is an underlying deficit strongly associated with relapse risk and impaired functional recovery. There is thus a critical need for a shift in the design and application of treatments for schizophrenia to more adequately address the lack of functional recovery and high relapse risk. The research proposed in this application is innovative because it represents a departure from the status quo of the current array of treatments and targets functional recovery and relapse prevention through an intervention aimed at improving resilience to stress. There are a number of proximal measures associated with stress reactivity including autonomic, endocrine, and immune system function measures that will be key indicators of treatment change in this paradigm shift. We propose to test this theory targeting stress reactivity by developing an intervention aimed at altering the stress response through mindfulness, as well as buffering against the negative effects of stress through meaningful coping strategies and positive affect. This should restore allostatic load and result in functional recovery (Bower et al., 2008; Hamilton et al., 2006; Mauss et al., 2011).

[figure not shown]

Figure 1. A pilot study of 10 schizophrenia (SCZ) probands, and 17 controls (CTL), aged 19.4 ± 3.5 , using the Montreal Imaging Stress Task (MST) was done in a laboratory setting (not in the scanner). Compared to CTLs, SCZ probands had abnormal reactivity to the 20-minute stressor (shaded area). CTLs showed the expected rise and fall of cortisol, decreased parasympathetic activity, and minimally increased sympathetic activity, with complete recovery following stressor termination. Patients showed blunted cortisol and parasympathetic responses and elevated, prolonged sympathetic reactivity.

